Preliminary correlation-interaction network analysis of 5 representative subjects were performed with the voxel-intensity time courses for a subject depicted (Figure 2A). This yielded spring-embedded network layouts that for each subject exhibited a small-world structure of focal clusters with short-range interactions connected by long-range edges (Figure 2B). A 3-D representation of cluster connectivity (Figure 2C) showed various clusters in the cerebellum connected to clusters in parietal, frontal and temporal lobes and to clusters in the limbic system mainly via the medial posterior brain regions (e.g. posterior cingulate).

[figure not shown]

Figure 2

Now that we have a better understanding of normal healthy micturition we plan to study brain activity in patients with neurogenic bladder (such as patients with multiple sclerosis) and voiding dysfunction. There is no similar report in the literature. In patients with multiple sclerosis, urinary symptoms are common sequel: urgency, urge incontinence, frequency, urinary retention (7, 8). These patients often undergo urodynamic testing and abnormalities are seen in almost all symptomatic cases. Common findings include neurogenic detrusor over-activity, detrusor sphincter dyssynergia and detrusor hypocontractility.

Clinical correlation between women with these chronic urologic problems and new discoveries at the level of CNS activity will give a better understanding of this disorder, leading to the development of more effective diagnostic and treatment modalities.

In addition the literature lacks any data regarding sensory effects of bladder medications used for neurogenic detrusor overactivity(NDO) or overactive bladder(OAB). A common and FDA approved treatment for these patients include use of Botulinum toxin A injected in the bladder. This is a routine

Brain Control of Voiding

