management for urinary symptom control in these patients. Despite having knowledge and data that Botulinum toxin A decreases the bladder contractility we have no human data how it affects the sensory efferent fibers to the brain and decreasing urgency and frequency. Our platform is a perfect model to study the effects of botulinum toxin A on sensory efferent fibers of the bladder and correlate that to the centers in the brain that respond to urgency and frequency. Thus we propose that patients who based on their clinical needs and exams are candidates for intravesical botulinum toxin A and have been a candidate in our study to have another fMRI with concurrent UDS about 8 weeks following their intravesical botulinum toxin A injection.

Purpose and Objectives

To perform functional MRI neuroimaging and data analysis on female subjects diagnosed with voiding dysfunction or neurogenic bladder during the act of micturition. Our goal with this pilot study is to determine whether BOLD signal changes on fMRI during voiding are substantial for data analysis. If so, data analysis will yield specific regions of the brain that are activated and/or deactivated during voiding. The second objective of this study is to determine whether concurrent urodynamics data gathered in the scanner can be correlated to fMRI data in order to elucidate simultaneous bladder function measurements with BOLD signal measurements.

Second objective of this study is to evaluate the sensory effects of intravesical injection of botulinum toxin A used for neurogenic detrusor activity.

Risk Category

(45 CFR 46.406) Category 3: Research involving greater than minimal risk and no prospect of direct benefit to the individual subject, but likely to yield generalizable knowledge about the subject's disorder or condition.

Research Design

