- Exclusive use of indwelling urethral or suprapubic catheter or other methods of urinary diversion
- Severity of neurologic illness: severe immobility, severe dyscoordination, cognitive impairment

STUDY PROCEDURE

Subjects will be recruited via bulletin board advertisement, web site and word of mouth.

All procedures are investigational. None of the following are part of standard clinical care.

There are no known risks to a subject's fetus. There is no known teratogenic risk associated with urodynamics or fMRI. Patients will be screened with a urine pregnancy test at enrollment and before fMRI scanning. Patients with a positive pregnancy test will be excluded from the study.

Procedure Visits:

1) Informed Consent and Enrollment

Patients will be screened with a history and physical, urinalysis and urine culture, and urine pregnancy test. Subjects will also be asked to fill out the following questionnaires: Urogenital Distress Inventory (UDI-6), Incontinence Impact Questionnaire (IIQ-7), and the Hamilton Anxiety Rating Scale (HAM-A). Patients will also be asked to fill out an fMRI safety screening questionnaire and demographics form.

After informed consent and enrollment, subjects will be scheduled for one or two visits:

2) Clinic Urodynamics Visit

Subjects diagnosed with neurogenic bladder or dysfunctional voiding have already undergone clinic urodynamics based on routine clinical care and will proceed to step 3. If there is a patient that would need a urodynamic study they will be instructed to arrive at The Methodist Hospital Department of Urology. This visit will consist of multichannel urodynamics in the clinic setting, so subjects can acclimate to the

Brain Control of Voiding

catheters and the testing situation. This visit will be 100% research. However, the test performed is one used by the urology clinic in daily clinical care. While the data collected will be for study use only, there is nothing experimental about the urodynamics procedure. Prior to catheter insertion, a dip stick urinalysis is performed to exclude bacteriuria.

3) fMRI Scanning Visit

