The second visit will be the fMRI scanning session at the Methodist Hospital. Subjects will be instructed to arrive 30 minutes prior to scanning. Subjects will have a dip stick urinalysis performed and a urine pregnancy test to confirm that they are not pregnant prior to the insertion of the catheters and the MRI. Urodynamics catheters will be inserted. After task instruction, subjects will be placed in the scanner. Task instruction consists of giving subjects directions to hold their urine, relax their pelvic muscles, and void will be conveyed to them via instructions printed on a screen they will see while in the scanner. Patients will also be instructed to squeeze a bulb in their hand if they experience claustrophobia or discomfort, and want to be removed from the scanner. Scanning will then begin.

After standard localizer and structural scans, the functional sequence and urodynamics will start. The bladder will be filled with sterile saline, as per urodynamics procedure. Subjects will be instructed (visually using a projection screen and mirror, standard procedure for the HNL) to hold their bladder, and then view a fixation cross for 30 seconds. They will be asked to indicate, via finger button, when their bladder is full. Subjects will then be instructed (again using a projection screen and mirror) to relax their pelvic floor muscles, and then to urinate. The experiment will conclude with the subject pressing the finger button to indicate they are finished urinating. At that point an instruction to relax will appear and then be replaced by a fixation cross that the subject will view it for 30 seconds and the experiment will be complete. The urodynamic and scanning cycle may be repeated up to 5 cycles.

4) repeat fMRI scanning visit:

This visit would only apply to the patients that clinically were a candidate for intravesical injection of botulinum toxin A and went on receiving it as a part of their routine care. If they agree, we would recruit them for a repeat fMRI scan just as detailed above about 8 weeks (+/- 4 weeks) following their botox injection. Urogenital Distress Inventory (UDI-6), Incontinence Impact Questionnaire (IIQ-7), and the Hamilton Anxiety Rating Scale (HAM-A) will be re-obtained at this visit.

Sample Size

How many subjects (or specimens, or charts) will be used in this study?

Local: 50 Worldwide: 50

Please indicate why you chose the sample size proposed:

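### Earlier botulinum toxin injections are neither restricted nor dated, so a woman's 'before' scan may itself be an on-toxin scan and the before/after difference may be biased toward zero

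*Combined protocol and SAP*

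**What the plan says.** Purpose and Objectives labels two different aims as second. The one at issue here is to "evaluate the sensory effects of intravesical injection of botulinum toxin A used for neurogenic detrusor activity".

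The design serves that aim with one feature. The background section proposes that suitable participants agree "to have another fMRI with concurrent UDS about 8 weeks following their intravesical botulinum toxin A injection". Study Procedure, item 4 (repeat fMRI scanning visit) opens that visit to participants who "clinically were a candidate for intravesical injection of botulinum toxin A and went on receiving it as a part of their routine care", and times it "about 8 weeks (+/- 4 weeks) following their botox injection". The three symptom and anxiety questionnaires are repeated at the same visit.

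The background presents the treatment as established in this population: "A common and FDA approved treatment for these patients include use of Botulinum toxin A injected in the bladder". It also describes it as routine "management for urinary symptom control in these patients".

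The Inclusion and Exclusion Criteria do not mention earlier toxin. Appendix D (Schedule of Events) places Patient History and Medication Review at Visit 1 only. Appendix E (demographics form) asks for medications now being taken and for surgical procedures with an approximate year. The Data Analysis section describes a voxel-wise general linear model and regressions on behavioral variables. It names no covariate, subgroup or sensitivity analysis for earlier toxin.

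**The concern.** A before/after comparison needs a 'before' that is free of the treatment. Here the injection that triggers the repeat visit need not be the woman's first, and no interval is set between an earlier injection and the first scan. The protocol treats 4 to 12 weeks after injection as the time to look for the drug's effect, yet a first scan may fall in that same window after an earlier injection. That woman would contribute two on-toxin scans, one of them labelled as baseline.

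Residual effect at the first scan makes it resemble the second, so the direction of the bias is known: toward no difference. There is no concurrent patient group to fall back on. The historical healthy women named under Research Design cannot stand in for a patient's own pre-injection state. The Sample Size section says the pilot data will help to power later studies, so an attenuated estimate would carry forward into their planning. Because no form asks for injection dates, the problem could not be detected from the study's own data.

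**Working it through.** The documents derive no effect size, power or number of pairs for this objective, so there is no figure to reproduce. The check has two parts.

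**1. Is there a safeguard?**

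- Inclusion and Exclusion Criteria: no condition on earlier toxin, no minimum interval.
- Repeat visit (Study Procedure, item 4): no first-injection condition. Window 8 − 4 = 4 weeks to 8 + 4 = 12 weeks.
- Appendix D: history and medication review at Visit 1, with no rule attached and no update at the first scan (Visit 3).
- Appendix E: an approximate year cannot place an injection against a window measured in weeks.
- Data Analysis: no adjustment for prior exposure.

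Nothing closes the gap.

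**2. What would carry-over do?**

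Let d be the true toxin effect on the imaging measure, f the share of paired women with an earlier injection, and c the average fraction of its effect they retain at the first scan. Assume that the later injection brings every woman to the same on-toxin level and that nothing else changes between sessions. Then:

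- mean at first scan = m + f·c·d
- mean at repeat scan = m + d
- expected difference = d(1 − f·c), so the proportional bias is f·c

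The documents give neither f nor c. With assumed values:

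| f | c | bias f·c | observed / true | pairs needed to keep power, 1/(1 − f·c)² |
|---|---|---|---|---|
| 0 | any | 0% | 1.00 | × 1.00 |
| 0.10 | 0.5 | 5% | 0.95 | × 1.11 |
| 0.25 | 0.5 | 12.5% | 0.875 | × 1.31 |
| 0.50 | 0.5 | 25% | 0.75 | × 1.78 |

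The last column holds the SD of the paired differences fixed.

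For scale only, take an assumed 20 pairs, standardized paired effect 0.5 and two-sided alpha 0.05. Power by normal approximation is Φ(0.5 × (1 − f·c) × √20 − 1.96):

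- no carry-over: Φ(2.236 − 1.96) = 0.61
- 12.5% attenuation: Φ(1.957 − 1.96) = 0.50
- 25% attenuation: Φ(1.677 − 1.96) = 0.39

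**Would excluding affected women be better?** Relative to no carry-over, signal-to-noise is √(1 − f) if all women with an earlier injection are dropped and 1 − f·c if everyone is kept (SD fixed):

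- f = 0.3, c = 0.5: √0.7 = 0.84 against 1 − 0.15 = 0.85
- f = 0.6, c = 0.5: √0.4 = 0.63 against 1 − 0.30 = 0.70
- f = 0.6, c = 1: 0.63 against 1 − 0.60 = 0.40

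Exclusion removes the bias but costs precision. It gains signal-to-noise only when retention is high.

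**The case against.** The strongest reply is that the protocol has indirect protection. Entry requires current lower urinary tract symptoms, and the repeat visit applies only to women whose clinical needs make them candidates and who then go on to be injected. A woman still well controlled by an earlier injection is less likely to meet those conditions. This stands as a reason to expect less carry-over. It does not rule it out: difficulty emptying alone satisfies the symptom criterion, and partial residual effect can coexist with symptoms.

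A second reply is that history, medications and procedures are already collected. That is true, and it narrows the gap to a date field and an analysis rule.

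A third is that this is a feasibility pilot with no alpha, power or decision rule, and that the Data Analysis section never writes down a before/after contrast. Also true. The contrast is inferred from the repeat scan and the repeated questionnaires, but no other stated purpose explains that visit.

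A reader might go further and infer that treated bladders also contaminate the first-objective voiding map. The documents do not support that as a fault: the target population is women with voiding dysfunction or neurogenic bladder, with no requirement that they be untreated. A reader might also take 12 weeks as the interval that guarantees a clean baseline. It is only the outer limit of a visit window; the documents state no duration of effect.

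**Conclusion.** The gap is real. The implied before/after comparison has no protection against an active earlier injection at the first scan, and any such carry-over biases it toward zero.

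The size is unknown. It is nil if no paired woman has a still-active earlier injection, and 5% to 25% in the illustrations with f from 0.10 to 0.50 and c = 0.5. Those values are assumptions, as are equal effect of successive injections and no other change between sessions.

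A reader might infer that carry-over is present and large, or that the study is set to declare no central sensory effect. Neither follows: nothing shows that any participant has an active earlier injection, and no such formal conclusion is planned. What the documents support is a bias of known direction and unknown size that the study's data, as specified, could not reveal.

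**What to change.** - At Visit 1, record the date of every earlier intravesical botulinum toxin injection, and update the record at Visit 3.
- Write the Visit 3 to Visit 4 comparison into the Data Analysis section. Pre-state that it is reported for all pairs and also by prior exposure: women with no earlier injection, or with a first scan outside an interval that the investigators justify in advance, against women with a first scan inside it.
- State that a null result in all pairs will be interpreted in the light of the pairs unexposed at baseline.

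Keeping all pairs and adding the split avoids discarding scans whose exclusion might lose more precision than it recovers.

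The cost is one history item, one extra analysis, and fewer pairs in the restricted comparison. The interval only classifies scans for analysis. No patient's treatment is changed, delayed or withheld.

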This is a pilot study. These experiments are novel, as there is currently no similar study in the literature. There is no way to predict numbers required in order to find statistically variations between arms of each experiment. Pilot data from this study will aid in powering future studies on the same topic. This study involving human subjects with both urodynamic and fMRI testing is complex, time-consuming, and expensive. Furthermore, no investigator has published previously regarding simultaneous urodynamics

Brain Control of Voiding

and fMRI. This protocol is for a feasibility study. Once the feasibility of our model is established, we can work on studying control groups.

Data Analysis

Provide a description of your plan for data analysis. State the types of comparisons you plan (e.g. comparison of means, comparison of proportions, regressions, analysis of variance). Which is the PRIMARY comparison/analysis? How will the analyses proposed relate to the primary purposes of your study?

The data analysis will be similar to other data analytic strategies carried out in the laboratory. It requires fairly complex analysis techniques and is thus difficult to summarize without going into lengthy details. Briefly, our data analysis will be as follows: We have made extensive use of a general linear model in analyzing and designing our fMRI experiments. To compare data from different subjects, the scan data from each subject must be transformed into a standard anatomical framework. We follow the approach of Frackowiak et al (1997), which analyzes the brain into small local volumes or “voxels”. The fMRI signal from each voxel is then subjected to the following transformation steps:

Analysis Step 1: Spatio-temporal normalization to a standard brain map, and smoothing to improve the signal-to-noise ratio.

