Analysis Step 2: Statistical analysis to determine the significance of the activity measured at each voxel. We use an established statistical framework [K.J. Friston, et al., Human Brain Mapping 2, 189-210 (1995); K.J. Friston, A.P. Holmes, K.J. Worsley, Neuroimage 10, 1-5 (1999)] in terms of a general linear model, which incorporates and formalizes the independent explanatory variables in our experiment. Given the variance of each parameter, we can construct a t-statistic as a measure of the significance of differences in the parameters estimated from the different experiments, at different voxels, or in different subjects. In practice, we construct a statistic out of a particular linear combination of the parameters that describes a quantity of interest. To express this mathematically, we define a contrast vector that specifies a linear combination of parameters. Then the t-statistic is the quantity of interest divided by its standard error. When we calculate a t-statistic at each voxel in an imaged brain, measuring the significance of a difference between parameters from different subjects or different experimental conditions, the resulting set is called a statistical parametric map. We use such maps to determine areas of significant activation in the brain during presentation of stimuli or performance of the task.

A linear regression analysis will also be employed to look for covariance of behavioral variables with observed brain activity. For instance, the degree of preference for an image or the amount of prior exposure to the stimulus can be entered into the analysis as explanatory variables for the brain activation. In this case, the degree to which behavioral variables cause linear changes in brain activity can be illustrated by fitting the estimated response to the observed time series of dynamic blood flow in the brain. The regions identified in this type of analysis will be used to generate “regions of interest”, smaller areas of voxels that can be analyzed without making assumptions regarding the underlying hemodynamics. In this analysis, the raw change in magnetic signal can be read out and compared across any variable of interest.

Brain Control of Voiding

Potential Risks/Discomforts

Risks with Pregnancy:

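### Analysis Step 2 declares significant brain regions from voxel-by-voxel tests with no whole-brain error control, and lets regions of interest be re-read against the variable that selected them

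*Combined protocol and SAP*

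**What the plan says.** The whole analysis plan is the Data Analysis section of the combined protocol and SAP. It opens by saying "The data analysis will be similar to other data analytic strategies carried out in the laboratory" and describes the method only in brief, with citations to a general linear model framework.

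- **Testing.** Analysis Step 2 is headed "Statistical analysis to determine the significance of the activity measured at each voxel". The t-statistics may compare "the parameters estimated from the different experiments, at different voxels, or in different subjects". Each is divided by its standard error, with no statement of whether that error is within or between subjects.
- **Reading the maps.** "We use such maps to determine areas of significant activation in the brain during presentation of stimuli or performance of the task". No alpha, height threshold, cluster rule or multiplicity correction appears anywhere in the document.
- **Regions of interest.** After the regression on behavioural variables: "The regions identified in this type of analysis will be used to generate" regions of interest, in which "the raw change in magnetic signal can be read out and compared across any variable of interest".
- **Primary analysis.** The form asks "Which is the PRIMARY comparison/analysis", and the reply does not name one. The task in Study Procedure, 3) fMRI Scanning Visit has hold, fixation, relax and void phases, but no baseline for the voiding contrast is chosen.
- **Promised output.** Purpose and Objectives says that, if the signal proves analysable, "data analysis will yield specific regions of the brain that are activated and/or deactivated during voiding".

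**The concern.** A whole-brain map contains thousands of tests. Without a stated rule, significance has no fixed meaning, the threshold can be chosen after the map is seen, and a reader cannot tell how many listed regions are chance.

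The region-of-interest step adds a second problem. If a region is kept because it correlates with a score, and its signal is then compared across that same score, the result is guaranteed to look strong. The Sample Size section says the pilot will help power later studies. It does not say which figures will be carried forward, so carry-over of an inflated effect is possible rather than planned.

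**Working it through.** **1. The plan's own figure.** The only figure is 50 subjects (Sample Size). No alpha, power, effect size or SD stands behind it, so there is nothing to reproduce. What follows shows the consequence of the gap under stated assumptions.

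**2. Simple count.** Assume 20,000 to 200,000 voxels. Expected false voxels = V × α. At α = 0.001 that is 20 to 200; at 0.05 it is 1,000 to 10,000. Treating the brain as R independent elements, each tested one-sided, the chance of at least one false positive is 1 − (1 − α)^R. At α = 0.001:

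- R = 100: 1 − 0.999^100 = 0.10
- R = 300: 0.26
- R = 1,000: 0.63

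**3. Simulated null maps.** Assumptions: smooth Gaussian noise, an ellipsoid with 68 × 84 × 58 mm semi-axes (21,693 voxels of 4 mm), 50 subjects, a correct one-sample t with 49 df, two-sided p<0.001 (|t| > 3.50), clusters of any size, and 1,500 maps per row.

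| Smoothness (FWHM) | Maps with a false cluster | Median false clusters | Same at p<0.0001 | 5% voxel-level threshold, \|t\| |
|---|---|---|---|---|
| 12 mm | 100% | 7 | 61% | 5.15 |
| 16 mm | 97% | 3 | 42% | 5.05 |
| 24 mm | 74% | 1 | 19% | 4.74 |

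Repeat runs gave 68% and 76% at 24 mm and 97% to 100% at the other two. A random-field calculation on the same ellipsoid gave about 100% / 99% / 79% at p<0.001. The count in step 2 is lower because it is one-sided and treats each element as a single test, which undercounts peaks in a smooth map. Every one of these p<0.001 figures exceeds 5%.

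**4. Re-reading a selected region.** In a voxel-wise regression on a score with n = 50, p<0.001 requires |r| > t/√(t² + 48) = 3.505/√(12.29 + 48) = 0.451. Significance at 0.05 requires only 2.01/√(4.04 + 48) = 0.28. Averaging voxels that each correlate above 0.451 in the same direction cannot bring the correlation of the average below 0.451, because the SD of an average is never larger than the average SD. So every same-data re-test passes 0.05 by construction. In the simulated null maps the largest cluster had a median |r| of 0.55 / 0.53 / 0.50 at 12 / 16 / 24 mm, with a true value of 0. Re-tested on independent data, null regions were significant in 4% to 6% of runs, as they should be.

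**5. Group error term.** Repeated cycles within a scan create both within- and between-subject variance. If only within-subject error were used, the true one-sided rate would be 1 − Φ(z/√(1 + r)), where r is the between/within variance ratio of a subject's estimate. For a nominal 0.001 (z = 3.09):

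- r = 0.25: 0.003
- r = 1: 1 − Φ(3.09/1.414) = 0.014
- r = 4: 0.084

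**6. Regions borrowed from the healthy subjects.** Research Design names the earlier healthy women as the control, and the background reports ten of them. In null maps of 10 healthy subjects and 50 patients, a region was selected where the healthy group was active and the two groups were then compared in it. The difference was falsely significant at 0.05 in 81% to 91% of one set of runs and 96% to 99% of another. Those data are therefore not independent for that comparison.

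**The case against.** - **It is a brief plan for a feasibility pilot.** It cites established frameworks and laboratory practice, region lists are conditional on usable signal, and no treatment decision hangs on them. This lowers the severity and stands. It does not give the word significant a definition: citing a modelling framework does not say which threshold this study will apply.
- **The percentages are hypothetical.** This also stands. Voxel size, smoothness and threshold are assumed, and having no minimum cluster size is an unfavourable case that the plan does not propose.
- **Circular testing is not planned.** The text says signal can be compared and mentions no p-value there. Its examples (liking for an image, earlier exposure to a stimulus) are not variables of this study, so the paragraph reads as general laboratory text. This stands in part: nothing excludes the selecting variable, and inflation of the displayed effect needs no p-value.

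A reader might infer that the maps will be read uncorrected, that the group analysis will use the wrong error term, or that most reported regions will be false. The documents support none of these. They leave the choices unstated, and the laboratory's usual practice cannot be checked here.

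**Conclusion.** The point holds as a gap in the plan: significance is claimed from whole-brain maps with no error control, and regions of interest can be read out against the effect that chose them. If maps were read at uncorrected p<0.001 with no cluster-size rule, roughly 70% to 100% of null maps would show a false cluster at 12 to 24 mm smoothness, or 10% to 63% under the independent-element count. A null region re-read on its own score would show a median |r| of about 0.5. These are illustrations, not predictions for this study.

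The unnamed primary contrast and the unstated error term are mainly missing detail in a brief plan. A baseline is available in the task, and a between-group comparator is named in Research Design. Both are worth settling in the same edit. Rating: cheap improvement.

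**What to change.** Add to Analysis Step 2:

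> A region is called significant only after a prespecified whole-brain 5% correction (for example cluster-level family-wise error with cluster-forming p<0.001). Cycles are combined into one contrast image per subject per visit, and group inference uses subject as the unit: one-sample t for patients, paired t for before versus after injection, two-sample t for patients versus the earlier healthy subjects. The voiding contrast and its baseline phase are named before group maps are viewed. Regions of interest taken from these maps are not re-tested against the variable or effect that selected them; they are fixed in advance, taken from data not used in the comparison, or reported descriptively and labelled as selected on the same data. Regions defined in the healthy subjects are not used for patient-versus-healthy comparisons.

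This needs no new visits, scans or subjects. The cost is that fewer or smaller regions reach significance. Under the cluster-level example the height stays at |t| of about 3.5 and a minimum cluster size is added: roughly 16 / 36 / 65 voxels of 4 mm at 12 / 16 / 24 mm smoothness, a rough estimate from 150 maps each. Under voxel-level correction with 50 subjects the threshold rises to about 4.7 to 5.2. The number of repeat-scan subjects is not given. If it were 20 (an assumption), a voxel-level paired map would need about 6.0 to 6.5, against 3.9 uncorrected.
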